8.6.3 Plan for Endocrine Disruption in Cancer Care

Rev. Add11

A longitudinal observational study is proposed to examine reproductive health biomarkers in a subgroup of participants (first 200 subjects who agree to participate in this part of study) in the EROS Trial. Participants will be asked to provide blood samples for laboratory correlates (AMH, FSH, TSH, TPO), indicating reproductive health, fertility status, and endocrine disruption. Blood samples will be obtained at baseline and periodically at 3, 6, 12, and 24 months from baseline visit on the study, which totals 8 blood draws. In addition, blood samples will be acquired in conjunction with chemotherapy (within one week of each regimen, prior to chemotherapy) or radiation therapy (within one week prior to the initiation of radiation therapy then every four weeks until the end of radiation treatment). This will increase the number of samples for that population as we attempt to

assess impact of chemotherapy on endocrine function. The hormonal levels at each measurement point will be summarized (by median and range) and plotted across time by marker. All analysis will be performed for patients with chemotherapy and without chemotherapy separately. To assess the impact of chemotherapy on endocrine function, a linear mixed-effect model will be used to make comparisons between the two groups with respect to each marker.

To determine the percent of females having significant endocrine disruption during chemotherapy, Table 7 below summarizes the abnormal level for each marker.

Table 7: Endocrine Markers and Associated Threshold Values for Endocrine Disruption

Marker	Age Range	Abnormal Range
FSH	15-55	≥ 23.0 mIU/mL
TPO	15-55	< 35 IU/mL
TSH	≤ 19	0.50-4.30 mIU/mL
	≥ 20	0.40-4.50 mIU/mL
AMH	≤ 19	0.76 – 11.34 ng/mL
	20-29	0.76- 11.34 ng/mL
	30-39	< 9.24 ng/mL
	40-49	< 4.50 ng/mL
	≤ 50	< 0.45 ng/mL

Quest Diagnostics Laboratory reference ranges

For each marker, the patient with the observed lab value falling into the abnormal range is considered to represent a case with endocrine disruption. Frequency and percentage (along with its 95% confidence interval) will be used to summarize patients with endocrine disruption during chemotherapy for each marker.

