1.7 Reproductive Health Related Endocrine Disruption in Cancer Care

Rev. Add10

We propose a 2-year observational study following tumor markers for fertility status and endocrine disruption of the first 200 individuals who agree to participate.

Primary Hypothesis

At least 80% of females will have significant endocrine disruption during chemotherapy.

Background

The sequelae of endocrine disruption may include loss of fertility. Although some cancer therapy modalities induce amenorrhea, many patients undergoing treatment remain fertile. After a short period of chemotherapy-induced amenorrhea, 50% of females younger than 35 years resume menstruation, whereas in older females the risk of amenorrhea is increased due to reduced follicular reserve.⁹ The absence of menstruation does not necessarily indicate lack of ovarian function. Additionally, the possibility of spontaneous recovery of ovarian function has been observed, particularly in cases of ovarian germ cell cancer. A study by Fossa found that cisplatin-based chemotherapy is followed by a recovery of ovarian function in almost all patients.⁹

For patients on chemotherapy who desire fertility, ovarian function should be reassessed periodically. Since menstrual activity is not a reliable index to assess ovarian function, various tests like FSH level, inhibin A or B levels or antimullerian hormone (AMH) and vaginal ultrasonography assessment for number of antral follicles can be used.¹⁰

Knowledge of the functional ovarian reserve may benefit females with cancer prior to making important decisions regarding treatment, fertility preservation, and contraception. An ideal marker for fertility status has not yet been identified. Recent literature (2009) indicates the best biochemical indicators of ovarian reserve are serum FSH levels, AMH and Inhibin B.¹¹ In the reproductive

endocrinology literature, AMH is emerging as the optimal marker to determine ovarian reserve and subsequent pregnancy success.¹² Experience with AMH in cancer survivors is limited, however this marker has potential as an indicator of ovarian function post chemotherapy.^{11,13} FSH as a marker may be less reliable as it is ovulatory cycle dependent and affected by tamoxifen and other hormonal therapies.¹³

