Additionally alterations in thyroid function have been noted in females with breast cancer with a baseline rate of autoimmune thyroid disease 2-3 times the general population.¹⁴ Thyroid function may be affected by chemotherapy and radiation treatment, particularly when treatment is localized to the vicinity of the thyroid.¹⁵ Such disruption may lead to symptoms that may affect quality of life indicators related to sexuality and sexual health. Repercussions of these effects remain an important aspect of research within oncology care. Given the available data, many questions remain unanswered; therefore, the laboratory ancillary included in this proposal would provide important data during the course of our primary study.

This data will provide a foundation for future research to aid prediction of fertility status throughout the course of cancer care and treatment.

This analysis will be performed at Quest Diagnostics.

Rev. Add9

1.8 Quality of Life (QOL) Assessment: Longitudinal Study of Sexuality in Females with Newly Diagnosed Cancer

Rev. Add11

We propose a prospective observational study performing interval sexuality surveys for reproductive aged females throughout 2 years post diagnosis of cancer.

Hypothesis

Primary Hypothesis: Cancer survivors' sexual function decreases during initial cancer treatment then increases with time after treatment completion.

Secondary Hypothesis: Cancer survivors have lower levels of satisfaction with their sex lives compared to the age-matched general population at baseline.

Background

Sexuality remains an important aspect of reproductive health that is greatly influenced by cancer diagnosis and treatment. The extent of impact of cancer diagnosis and treatment is poorly understood. Sexuality encompasses gender roles, patterns of affection, social and family roles, and genital sex, and affects a survivor physically, psychologically, and emotionally.¹⁶ It should be understood that sexuality is "an ever-changing, lived experience affecting the way in which people view themselves, their body and their ability to intimately connect with significant others throughout life, rather than limiting it to fertility status or capacity for sexual intercourse."¹⁷

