3.1 Eligibility Criteria

Rev. 11/17	_____ 3.1.1	Female patients presenting with initial diagnosis of any type of cancer, including patients with DCIS.
Rev. Add8	_____ 3.1.2	Patients must not have initiated chemotherapy, radiation therapy or endocrine therapy prior to registration to this study.
Rev. 11/17	_____ 3.1.3	Patients must not have had a prior hysterectomy, bilateral oophorectomy or sterilization of any method.
Rev. Add9	_____ 3.1.4	Patients must be pre-menopausal patients within the reproductive age range of 15-55 years. Please note, pre-menopausal will be defined as females meeting the following criteria: 
• Patients not currently on hormonal contraception with the presence of menses in the past 6 months.• If no menstruation in the past 6 months, without hormonal manipulation, then confirmed FSH < 23mIU/mL• If age < 47 years and on hormonal contraception, then patient will be eligible regardless of menstrual history• If age ≥ 47 years and on hormonal contraception, then FSH confirmed < 23mIU/mL
Rev. Add10	_____ 3.1.5	Pregnant females are eligible to participate in this study.
Rev. Add10	_____ 3.1.6	Patients must have the cognitive ability to participate in the study.

Rev. 11/17 4. CTEP Registration Procedures

Rev. Add8
Rev. Add11

Food and Drug Administration (FDA) regulations and National Cancer Institute (NCI) policy require all individuals contributing to NCI-sponsored trials to register and to renew their registration annually. To register, all individuals must obtain a Cancer Therapy Evaluation Program (CTEP) Identity and Access Management (IAM) account (<https://ctepcore.nci.nih.gov/iam>). In addition, persons with a registration type of Investigator (IVR), Non-Physician Investigator (NPIVR), or Associate Plus (AP) must complete their annual registration using CTEP's web-based Registration and Credential Repository (RCR) (<https://ctepcore.nci.nih.gov/rcr>).

RCR utilizes five person registration types.

- IVR — MD, DO, or international equivalent;
- NPIVR — advanced practice providers (e.g., NP or PA) or graduate level researchers (e.g., PhD);
- AP — clinical site staff (e.g., RN or CRA) with data entry access to CTSU applications (e.g., Roster Update Management System (RUMS), OPEN, Rave,);
- Associate (A) — other clinical site staff involved in the conduct of NCI-sponsored trials; and

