7. Pregnancy Test requirements. All patients must be counseled about pregnancy precautions, risks of fetal exposure and other risk as per standard of care. Pregnancy tests should be administered at Baseline, 3, 6, 12, and 24 months from Baseline Visit and within one (1) week prior to each chemotherapy regimen. For patients on radiation therapy (RT) alone, pregnancy tests should be administered within one (1) week prior to the initiation of radiation therapy then every four (4) weeks until the end of radiation treatment. For patients who aged past 55 after enrollment may discontinue pregnancy tests if menopause is confirmed FSH < 23mIU/mL. Patients who have had a hysterectomy after enrollment may also discontinue pregnancy tests. Pregnant patients may discontinue pregnancy tests until delivery

Rev. Add10 8. If patient is pregnant or has been pregnant since her last study visit, one Pregnancy Supplement Form should be completed for each pregnancy.

9. Interview done after visit with the provider.

10. Study surveys should be completed at the beginning of each regimen of cancer treatment. For patients undergoing chemotherapy, surveys should be administered within one (1) week prior to each chemotherapy regimen. For patients on radiation therapy (RT) alone, surveys should be administered within one (1) week prior to the initiation of radiation therapy then every four (4) weeks until the end of radiation treatment. Patients receiving both chemotherapy and RT must follow the chemotherapy reporting schedule; if patient's treatment overlaps (+/- 2 weeks), the questionnaires do not have to be repeated.

Rev. Add10 11. Sites must complete the study surveys within the following windows:

- 3-month visit: +/- one month
- 6-month visit: +/- one month
- starting from 12-month visits: +/- 2 months

12. If there is an overlap (+/- 2 weeks) of visits at 3, 6, 12, and 24 months and visits relating to chemotherapy or RT, the Medical Record Abstraction-Follow up, Patient Follow-up Interview, the Sexual Function Survey and the Pregnancy Test only need to be completed once at the 3, 6, 12, and 24 month visits and not at the chemotherapy or RT visits.

13. The term 'regimen' is defined as anytime a patient starts a new course of medical treatment

Table 2. Biological Sample Submissions

NOTE: Effective March 10, 2021 the endocrine marker sub-study is closed to further accrual. This sub study has met its targeted accrual goal.

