8.6.4 Plan for Longitudinal Study of Sexuality

Measurement of PROMIS Sexual Function Survey Brief Profile v1.0 - Female will be used to evaluate the hypotheses that (1) cancer survivors' sexual function decreases during primary cancer treatment then increases after treatment completion and (2) cancer survivors have lower levels of satisfaction with their sex lives compared to the age-matched general population at baseline. All patients recruited for the EROS study will be included in this part of analysis. Data collected in PROMIS Sexual Function Survey Brief Profile v1.0 - Female in the EROS study will be summarized and plotted across time with respect to each of the subdomains (global satisfaction with sex life, interest in sexual activity, lubrication, vaginal discomfort, and orgasm). A linear mixed-effect model will be used to study changes in each of the subdomain scores of PROMIS Sexual Function Survey Brief Profile v1.0 - Female over time, with institution as the random effect (by stratum and across all patients if there is no difference between strata). For the secondary hypothesis, our comparative group is the

Rev. Add9

Rev. Add8

age-matched population of non-cancer females in the reproductive age range surveyed by the Duke Clinical Research Institute. The collaborator at Duke Clinical Research Institute will provide summary data on age-matched non-cancer patients. The PROMIS study uses a *T* score method with a mean of 50 and a standard deviation of 10. Results from the Sexual Function Survey in the EROS trial will be transformed into *T* scores as well then comparison between the groups will be performed using the two-sample *t* test.

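### Chemotherapy-triggered blood draws and surveys come before each regimen, and neither longitudinal analysis separates pre-exposure, on-treatment and post-treatment values

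*Combined protocol and SAP*

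**What the plan says.** The endocrine hypothesis in Section 1.7 is: "At least 80% of females will have significant endocrine disruption during chemotherapy". Section 8.6.3 reports a frequency, percentage and 95% confidence interval for this, marker by marker. It also compares chemotherapy with no-chemotherapy patients in a linear mixed model.

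Blood is drawn at baseline and at 3, 6, 12 and 24 months. In addition, "blood samples will be acquired in conjunction with chemotherapy (within one week of each regimen, prior to chemotherapy". Section 8.6.3 presents these extra draws as serving the assessment of chemotherapy's effect on endocrine function. Table 1 footnote 10 (Section 7) gives the matching survey rule: "surveys should be administered within one (1) week prior to each chemotherapy regimen". Sections 5.7.1 and 7 define the trigger: "The term 'regimen' is defined as anytime a patient starts a new course of medical treatment". RT-alone patients are measured before RT and then every four weeks until it ends. Patients having both modalities follow the chemotherapy schedule.

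At entry (Section 3.1), "Patients must not have initiated chemotherapy, radiation therapy or endocrine therapy prior to registration to this study".

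For sexual function, Section 8.6.4 tests whether "sexual function decreases during primary cancer treatment then increases after treatment completion". Section 1.8 words it almost identically. The analysis is: "A linear mixed-effect model will be used to study changes in each of the subdomain scores", over time, with institution as the random effect.

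**The concern.** Both hypotheses are defined by treatment phase: abnormal values while on chemotherapy, and a fall during primary treatment followed by a rise after it. For a woman with one regimen, however, the only measurement that chemotherapy triggers precedes her first dose. Because entry requires no earlier chemotherapy, RT or endocrine therapy, that measurement repeats baseline as far as those exposures go.

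The analysis sections do not correct for this. Section 8.6.3 does not say which draws count as during chemotherapy, or how several values in one patient make her a case. Neither mixed model names a term for being before, on or past treatment. At stake are the percentage set against the 80% hypothesis, the chemotherapy comparison for each marker, and the two sexual-function contrasts.

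**Working it through.** The documents give no power or precision figure for either sub-study that depends on this timing, so there is none to reproduce. The check counts scheduled samples by phase, then sizes the possible bias.

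**1. Samples by phase for one regimen.** From the documents: five calendar draws (baseline, 3, 6, 12, 24 months) plus one pre-regimen draw, so 5 + 1 = 6. (Section 8.6.3 states a total of eight calendar draws. That mismatch is a separate matter.) Baseline and the pre-regimen draw are pre-exposure, so 2 of 6. Assumed: chemotherapy starts s weeks after baseline and lasts D weeks, and visits fall at nominal weeks 13, 26, 52 and 104. A visit is on treatment if s < visit week ≤ s + D.

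| D (weeks) | s=1 | s=2 | s=4 | s=6 | s=8 |
|---|---|---|---|---|---|
| 9 | 0 | 0 | 1 | 1 | 1 |
| 12 | 1 | 1 | 1 | 1 | 1 |
| 16 | 1 | 1 | 1 | 1 | 1 |
| 20 | 1 | 1 | 1 | 2 | 2 |
| 24 | 1 | 2 | 2 | 2 | 2 |
| 26 | 2 | 2 | 2 | 2 | 2 |

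So 0 to 2 of the six samples are on chemotherapy, 2 are before it and 2 to 4 after it. The visit windows (±1 month at 3 and 6 months, Table 1 footnote 11) can move a visit into or out of the course. If all six values entered the endocrine model with equal weight, 2/6, or one third, of the chemotherapy group's values would carry no chemotherapy effect.

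**2. Bias with one value per patient.** Let f be the share of patients whose counted value is really pre-exposure, p0 the pre-exposure abnormal rate (assumed 5% to 30%), and 80% the true on-treatment rate. Observed rate = f × p0 + (1 − f) × 0.80.

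- f = 0.25: 0.25 × 0.05 + 0.75 × 0.80 = 61%, up to 0.25 × 0.30 + 0.60 = 68%.
- f = 0.50: 43% to 55%.
- f = 1: 5% to 30%.

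The 95% half-width at 80% is 1.96 × √(0.8 × 0.2 / 200) = 5.5 points for n = 200 and 7.8 points for n = 100. The f that shifts the estimate by the n = 200 half-width is 0.055 / (0.80 − p0), or about 7% at p0 = 5% and 11% at p0 = 30%.

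**3. Bias under an any-abnormal-value rule.** For a patient who has an on-treatment value, adding a pre-exposure value can only make her a case, never remove her. If the two values are independent, the observed rate is 1 − (1 − p0)(1 − 0.80): 1 − 0.95 × 0.20 = 81% at p0 = 5%, and 1 − 0.70 × 0.20 = 86% at p0 = 30%. If every woman abnormal beforehand is also abnormal on treatment, it stays at 80%.

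**4. Sexual function.** Section 8.6.4 hypothesises two contrasts: on treatment against before, and the course after completion. The model's only named time element is change over time, and Section 8.6.1 shows that treatment ranges over chemotherapy, RT, surgery and combinations. At any one visit some women are on treatment and others past it, so no coefficient in the model as described equals either contrast.

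**The case against.** The plan nowhere says that pre-regimen draws will be counted as on-treatment values; they are additional to the calendar draws. Most single-course patients in the table above have one or two on-treatment visits. RT-alone patients are measured during RT. Section 8.6.3 keeps chemotherapy and no-chemotherapy patients apart. If sites read course as cycle, only the first pre-regimen measurement is pre-exposure. The sexual-function hypothesis concerns all primary treatment, not chemotherapy alone. All of this stands and limits the point.

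A reader might infer that the sexual-function pattern could not be seen at all. The documents do not support that: no straight-line time trend is specified, and Section 8.6.4 plots scores across time. In a simulation with assumed inputs (20% surgery only, 15% RT alone, 40% chemotherapy, 25% both; a true fall of 6 T points recovering to −1 over 12 months), mean changes at baseline, 3, 6, 12 and 24 months were 0, −5.8, −5.2, −2.9 and −1.0. With visit as a category, the fall and the rise both show. They are blurred, however. About 31% of women were still on treatment at 6 months, so the −5.2 mixes women at −6 with women past treatment averaging about (−5.2 + 0.31 × 6) / 0.69 = −4.8.

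What the objection does not remove is that on-chemotherapy values occur only by coincidence of dates, that the first pre-regimen value is not excluded under either reading of course, and that keeping the two treatment groups apart does not separate phases within the chemotherapy group.

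**Conclusion.** The point holds as a design and analysis weakness that should be corrected. The chemotherapy-triggered measurements precede exposure for a first or only regimen, and neither analysis separates treatment phases. As written, the endocrine comparison can be diluted by pre-exposure values, the during-chemotherapy percentage can be biased, and the two sexual-function contrasts are not directly estimated.

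The size depends on quantities the documents do not give: f, p0, course length and the patient-level rule. Under the assumptions above the shift runs from 12 to 19 points downward at f = 0.25 (80 − 68 and 80 − 61) to as much as 6 points upward under an any-abnormal-value rule (86 − 80).

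A reader might infer that the 80% hypothesis is bound to fail because of timing. The documents do not support this, because the direction depends on the unstated patient-level rule. Nor can p0 be presumed low: the ranges in Table 7's abnormal column are described by the table's own note as laboratory reference ranges. A reader might also infer that both models run on visit month. Section 8.6.3 names no time variable, and Section 8.6.4 says only that change is studied over time. Section 8.1 places endpoint details in Addendum II, which is not in the combined document; any date rule there would need to be carried into these sections.

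**What to change.** In Sections 8.6.3 and 8.6.4, classify every sample and survey by its date against the first and last treatment dates: pre-treatment, on treatment, or months since completion. Say how surgery-only patients are classified.

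- **Section 8.6.3:** count disruption during chemotherapy only from samples dated after the first chemotherapy dose and before completion. State how several values make a patient a case, and how patients with no on-treatment sample are handled. Add time-varying treatment phase to the mixed model.
- **Section 8.6.4:** add time-varying treatment phase, and test on-treatment minus pre-treatment and the change after completion.

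Confirm first that the Medical Record Abstraction forms capture treatment start and stop dates; their content is not shown in the documents. If they do, the cost is analysis-plan text and programming, with no new visits or samples. The downside is that fewer values count as on treatment, so those intervals are somewhat wider.

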Serum specimens should continue to be collected from previously enrolled patients that have consented to provide serum specimens at the time points outlined below.

Do not submit serum specimens from patients registered to E1Q11 after March 10, 2021.

NOTE: THIS SECTION APPLIES TO BOTH STUDY ARMS.

Blood samples should be submitted for the endocrine markers as outlined in Section 9. Submit only from patients who have given written consent to participate in the optional laboratory studies.

NOTE: It is required that biological sample submissions be logged into the ECOG-ACRIN Sample Tracking System (STS) for purposes of monitoring compliance.

NOTE: Institutions must complete and submit the Quest Diagnostics Sub-Account Information Sheet ([Appendix III](#)) to create their study specific account number in order to obtain supplies and arrange for courier service for the collection of the blood samples. See Section 9 for further instructions.

Biological Materials	Day of Registration [prior to treatment] ¹	Within One Week Prior to Start of Each Chemotherapy Regimen or Every Four Weeks during RT ¹	At the end of 3, 6, 12, 24 Months from Baseline Visit
From Patients Who Answer "Yes" to "I agree to participate in the laboratory research studies that are being done as part of this clinical trial."³			
Serum (one 7.5mL red top tube) ^{2,3,4}	X	X	X
Serum, SST (one 7.5mL red/black top tube) ^{2,3,4}	X	X	X

1. For patients undergoing chemotherapy, blood samples will also be collected in conjunction with chemotherapy within one (1) week prior to the start of each chemotherapy regimen. For patients undergoing radiation therapy (RT) alone, blood samples will be collected within one (1) week prior to the initiation of radiation therapy and every four (4) weeks until the end of radiation treatment.
2. When possible, blood draws will be timed with the collection of blood draws for routine clinical purposes thus minimizing participant burden.
3. Ship blood samples to Quest Diagnostics as outlined in Section 9.
4. Supplies are available for the collection of the blood samples.

Rev. 11/17	8. Statistical Considerations

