9.2 Sample Submission Schedule

Blood samples are being collected for the correlative studies outlined in Section [1.7](#) and analyzed by Quest Diagnostics.

NOTE: Results of these laboratory tests will not be returned to the institutions or reported to the patient.

NOTE: Blood samples should be collected as outlined in the table and sections below.

Rev Add 11

Biological Materials	Day of Registration [prior to treatment] ¹	Within One Week Prior to Start of Each Chemotherapy Regimen or Every Four Weeks during RT ¹	At the end of 3, 6, 12, 24 Months from Baseline Visit

From Patients Who Answer "Yes" to "I agree to participate in the laboratory research studies that are being done as part of this clinical trial."³
			
Serum (one 7.5mL red top tube) ²	X	X	X
Serum, SST (one 7.5mL red/black top) ²	X	X	X

1. For patients undergoing chemotherapy, blood samples will also be collected in conjunction with chemotherapy within one (1) week prior to the start of each chemotherapy regimen. For patients undergoing radiation therapy (RT) alone, blood samples will be collected within one (1) week prior to the initiation of radiation therapy and every four (4) weeks until the end of radiation treatment.
2. When possible, blood draws will be timed with the collection of blood draws for routine clinical purposes thus minimizing participant burden.

Rev. 5/17

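### The chemotherapy versus no-chemotherapy comparison in 8.6.3 does not separate or adjust for radiation, so its TSH and TPO results may be confounded by RT

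*Combined protocol and SAP*

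**What the plan says.** Section 8.6.3 sets out the analysis of AMH, FSH, TSH and TPO in a sub-study of 200 patients. It fixes the grouping: "All analysis will be performed for patients with chemotherapy and without chemotherapy separately". The stated purpose of the contrast is to measure what chemotherapy does to endocrine function, and the method is that "a linear mixed-effect model will be used to make comparisons between the two groups with respect to each marker". No RT term, RT group or other covariate is named.

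Four other places bear on this.

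- **Section 1.7** gives the background on the thyroid: "Thyroid function may be affected by chemotherapy and radiation treatment, particularly when treatment is localized to the vicinity of the thyroid".
- **Section 7, Table 2, footnote 1, and section 9.2** give RT-alone patients their own sampling, which runs for the whole RT course: "blood samples will be collected within one (1) week prior to the initiation of radiation therapy and every four (4) weeks until the end".
- **Section 7, Table 1, footnote 10** shows that some patients have both treatments: "Patients receiving both chemotherapy and RT must follow the chemotherapy reporting schedule".
- **Section 8.6.1** adjusts the contraception-usage models for treatment type at four levels (chemotherapy, RT, surgery, combination). Section 8.6.3 does not carry this variable over.

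**The concern.** The comparison is not randomised. How patients are classified and what the model adjusts for are its only protection against other treatments that move the same markers. RT is such a treatment by the protocol's own account, at least for the thyroid, and any cancer type is eligible (section 3.1.1), so fields near the thyroid can occur.

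A yes/no chemotherapy split places RT-alone patients beside surgery-only patients in the comparator, and places chemotherapy-plus-RT patients in the chemotherapy group. If the share receiving RT differs between the groups, part of any RT effect on TSH or TPO is credited to, or taken from, chemotherapy. The planned output gives a reader no means of telling how much. RT-alone patients are sampled on a schedule of their own, yet no analysis treats them as a group.

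**Working it through.** The documents give no effect size, power or precision for this contrast, so there is no planned figure to reproduce. The check is whether the stated comparison recovers the chemotherapy effect when RT also acts.

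**Inputs from the documents.** Two groups by chemotherapy and no RT term (8.6.3); RT possible in both groups (section 7, Table 1, footnote 10, and Table 2, footnote 1); a possible RT effect on thyroid function (1.7); 200 patients (8.6.3).

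**Assumed inputs, not in the documents.** Let C be the mean shift in a marker caused by chemotherapy and rC the shift caused by RT, with effects adding. Let q be the RT share among patients without chemotherapy and s the share among patients with it. Ranges used: r = 0.25 to 1.0, q = 0.1 to 0.5, s = 0 to 0.7.

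**Formula.** Mean shift with chemotherapy: C + s·rC. Mean shift without: q·rC. The difference is C[1 + r(s − q)], so

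observed / true = 1 + r(s − q).

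**Results.**

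| r | q | s = 0 | s = 0.3 | s = 0.7 |
|---|---|---|---|---|
| 0.25 | 0.3 | 0.925 | 1.00 | 1.10 |
| 0.5 | 0.1 | 0.95 | 1.10 | 1.30 |
| 0.5 | 0.3 | 0.85 | 1.00 | 1.20 |
| 0.5 | 0.5 | 0.75 | 0.90 | 1.10 |
| 1.0 | 0.1 | 0.90 | 1.20 | 1.60 |
| 1.0 | 0.3 | 0.70 | 1.00 | 1.40 |
| 1.0 | 0.5 | 0.50 | 0.80 | 1.20 |

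For r = 0.5 and q = 0.3: 1 + 0.5(0 − 0.3) = 0.85; 1 + 0.5(0.3 − 0.3) = 1.00; 1 + 0.5(0.7 − 0.3) = 1.20. Over the whole assumed range the ratio runs from 0.50 to 1.60, and it is exactly 1.00 whenever s = q. If RT moves a marker in the opposite direction to chemotherapy, r is negative and the errors change sign.

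**Effect on power where the contrast is attenuated.** These figures assume a simple comparison of two means, 200 patients, two-sided alpha 0.05 and a true standardised effect of 0.5.

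| Ratio | Split 100/100 | Split 60/140 |
|---|---|---|
| 1.00 | 94% | 90% |
| 0.85 | 85% | 79% |
| 0.70 | 70% | 62% |
| 0.50 | 42% | 37% |

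Where the ratio exceeds 1, the cost is an overstated chemotherapy effect.

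**Would removing RT-alone patients from the comparator suffice?** That sets q = 0 and leaves 1 + r·s. This is further from 1 than the present plan whenever s > q/2. At r = 0.5, q = 0.3 and s = 0.3, the plan gives 1.00 and the reduced comparator gives 1 + 0.5 × 0.3 = 1.15. RT has to be handled in both groups.

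**The case against.** The strongest reply is that bias has not been shown. Chemotherapy patients may also receive RT; if the shares are similar the contrast is close to right, and the documents give no shares. That stands. A reader might infer that RT-alone patients in the comparator must pull the chemotherapy effect toward zero. This holds only if few chemotherapy patients receive RT and RT acts in the same direction, and neither is documented. Equally, nothing in 8.6.3 secures or checks balance.

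Second, the source is narrow. Section 1.7 speaks of a possible effect on the thyroid, mainly from nearby fields, and does not say that radiation changes AMH or FSH. A reader might extend the point to the ovarian markers; the documents do not support that, and it is limited here to TSH and TPO.

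Third, a reader might infer that the four-weekly draws give RT-alone patients extra weight in the comparator. That does not follow. In a mixed model, correlated repeat draws do not add weight in proportion to their number, and the baseline and pre-RT draws precede exposure. The extra draws are not themselves a source of bias.

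Fourth, 8.6.3 summarises and plots levels at every measurement point, so the RT-timed points among patients without chemotherapy do describe RT-alone patients. This is fair as far as it goes, but at 3, 6, 12 and 24 months these patients are pooled with those who had neither treatment.

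Last, covariates may be unstated rather than excluded, and Addendum II, which section 8.1 cites for endpoint details, is not in the text supplied. However, 8.6.3 describes this analysis itself, does not defer to that addendum, and fixes a two-way grouping.

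**Conclusion.** The point holds as a risk of confounding by RT in the TSH and TPO contrasts, created by a stated grouping rule. Its size and direction cannot be determined from the documents. Under the additive model the observed contrast could be attenuated, correct or inflated: 0.85 to 1.20 times the truth in the central example, and 0.50 to 1.60 over the full range, with r, q and s all assumed.

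The consequence is bounded. This is a supporting, non-randomised comparison within a correlative objective. A reader might infer that the sub-study's main question is compromised. It is not: the primary hypothesis in section 1.7, that 80% or more of patients show disruption while on chemotherapy, is assessed in 8.6.3 by a proportion with its confidence interval and involves no comparator. The change is still worth making, because the comparison is to be reported as a chemotherapy effect and the correction lies in the analysis alone.

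**What to change.** In section 8.6.3:

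1. State how RT-alone and chemotherapy-plus-RT patients are classified.
2. Fit chemotherapy and RT as separate terms in the linear mixed-effect model. Under the additive model above, this returns the ratio to 1.00. Alternatively, use the four-level treatment variable of 8.6.1. In that case define its combination level, because as written it does not show whether a combination includes chemotherapy, RT or both.
3. Summarise RT-alone patients as their own group, using their pre-RT and four-weekly draws.
4. Keep the two-way chemotherapy split as a sensitivity analysis, and report the RT share in each group beside it.

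The cost is analysis-plan wording and a somewhat wider interval for the chemotherapy effect. No new data should be needed, since 8.6.1 already requires treatment type to be known. The abstraction forms are not in the documents, so whether they record the RT field is unknown, and the fix does not depend on it.
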